5.3.5.13 Clinical Outcome Assessment Data

Adverse event reports will not be derived from COA data by the Sponsor, and safety analyses will not be performed using COA data, except for the C-SSRS. If any responses suggestive of a possible adverse event are identified during administration of the C-SSRS, the investigator will determine whether the criteria for an adverse event have been met, and if so, will report the event on the Adverse Event eCRF.

5.4 IMMEDIATE REPORTING REQUIREMENTS FROM INVESTIGATOR TO SPONSOR

Certain events require immediate reporting to allow the Sponsor to take appropriate measures to address potential new risks in a clinical trial. The investigator must report such events to the Sponsor immediately; under no circumstances should reporting take place more than 24 hours after the investigator learns of the event. The following is a list of events that the investigator must report to the Sponsor within 24 hours after learning of the event, regardless of relationship to study drug or [¹⁸F]GTP1 radioligand or an amyloid radioligand:

- Serious adverse events (defined in Section 5.2.2; see Section 5.4.2 for details on reporting requirements)
- Adverse events of special interest (defined in Section 5.2.3; see Section 5.4.2 for details on reporting requirements)
- Pregnancies (see Section 5.4.3 for details on reporting requirements)

The investigator must report new significant follow-up information for these events to the Sponsor immediately (i.e., no more than 24 hours after becoming aware of the information). New significant information includes the following:

- New signs or symptoms or a change in the diagnosis
- Significant new diagnostic test results
- Change in causality based on new information
- Change in the event's outcome, including recovery
- Additional narrative information on the clinical course of the event

Investigators must also comply with local requirements for reporting serious adverse events to the local health authority and IRB/EC.

5.4.2 Reporting Requirements for Serious Adverse Events and Adverse Events of Special Interest

5.4.2.1 Events That Occur prior to Initiation of Study Drug or [¹⁸F]GTP1 Radioligand or an Amyloid Radioligand

After informed consent has been obtained but prior to initiation of study drug or [¹⁸F]GTP1 radioligand or an amyloid radioligand, only serious adverse events caused by a protocol-mandated intervention should be reported. The paper Clinical Trial Serious Adverse Event/Adverse Event of Special Interest Reporting Form provided to investigators should be completed and submitted to the Sponsor or its designee immediately (i.e., no more than 24 hours after learning of the event), by scanning and emailing the form using the email address provided below:

Email address: [contact]

5.4.2.2 Events That Occur after Initiation of Study Drug or [¹⁸F]GTP1 Radioligand or an Amyloid Radioligand

After initiation of study drug or [¹⁸F]GTP1 radioligand or an amyloid radioligand, serious adverse events and adverse events of special interest will be reported until 12 weeks after the final dose of study drug or 4 days after the final dose of [¹⁸F]GTP1 radioligand or an amyloid radioligand, whichever is longer. Investigators should record all case details that can be gathered immediately (i.e., within 24 hours after learning of the event) on the Adverse Event eCRF and submit the report via the electronic data capture (EDC) system. A report will be generated and sent to Safety Risk Management by the EDC system.

In the event that the EDC system is unavailable, the paper Clinical Trial Serious Adverse Event/Adverse Event of Special Interest Reporting Form provided to investigators should be completed and submitted to the Sponsor or its designee immediately (i.e., no more than 24 hours after learning of the event), by scanning and emailing the form using the email address provided in Section 5.4.2.1. Once the EDC system is available, all information will need to be entered and submitted via the EDC system.

Instructions for reporting serious adverse events that occur > 12 weeks after the final dose of study treatment or 4 days after the final dose of [¹⁸F]GTP1 radioligand or an amyloid radioligand, whichever is longer, are provided in Section 5.6.

5.4.3 Reporting Requirements for Pregnancies

5.4.3.1 Pregnancies in Female Patients

Female patients of childbearing potential will be instructed to immediately inform the investigator if they become pregnant during the study or within 9 weeks after the final dose of study drug or 4 days after the final dose of [¹⁸F]GTP1 radioligand or an amyloid radioligand, whichever is longer. A paper Clinical Trial Pregnancy Reporting Form should be completed and submitted to the Sponsor or its designee immediately (i.e., no more than 24 hours after learning of the pregnancy), by scanning and emailing the form using the email address provided in Section 5.4.2.1. Pregnancy should not be recorded on the Adverse Event eCRF. The investigator should discontinue study drug and counsel the patient, discussing the risks of the pregnancy and the possible effects on the fetus. Monitoring of the patient should continue until conclusion of the pregnancy. Any serious adverse events associated with the pregnancy (e.g., an event in the fetus, an event in the mother during or after the pregnancy, or a congenital anomaly/birth defect in the child) should be reported on the Adverse Event eCRF. In addition, the investigator will submit a paper Clinical Trial Pregnancy Reporting Form when updated information on the course and outcome of the pregnancy becomes available.

5.4.3.2 Pregnancies in Female Partners of Male Patients

Male patients will be instructed through the Informed Consent Form to immediately inform the investigator if their partner becomes pregnant during the study or within 9 weeks after the final dose of study drug or 4 days after the final dose of [¹⁸F]GTP1 radioligand or an amyloid radioligand, whichever is longer. A paper Clinical Trial Pregnancy Reporting Form should be completed and submitted to the Sponsor or its designee immediately (i.e., no more than 24 hours after learning of the pregnancy), by scanning and emailing the form using the email address provided in Section 5.4.2.1. Attempts should be made to collect and report details of the course and outcome of any pregnancy in the partner of a male patient exposed to study drug. When permitted by the site, the pregnant partner would need to sign an Authorization for Use and Disclosure of Pregnancy Health Information to allow for follow-up on her pregnancy. If after the authorization has been signed, the investigator would submit a paper Clinical Trial Pregnancy Reporting Form when updated information on the course and outcome of the pregnancy becomes available. An investigator who is contacted by the male

patient or his pregnant partner may provide information on the risks of the pregnancy and the possible effects on the fetus, to support an informed decision in cooperation with the treating physician and/or obstetrician.

5.4.3.3 Congenital Anomalies/Birth Defects and Abortions

Any congenital anomaly/birth defect in a child born to a female patient exposed to study drug or [¹⁸F]GTP1 radioligand or an amyloid radioligand or the female partner of a male patient exposed to study drug or [¹⁸F]GTP1 radioligand or an amyloid radioligand should be classified as a serious adverse event, recorded on the Adverse Event eCRF, and reported to the Sponsor immediately (i.e., no more than 24 hours after learning of the event; see Section 5.4.2).

A spontaneous abortion should be classified as a serious adverse event (as the Sponsor considers abortions to be medically significant), recorded on the Adverse Event eCRF, and reported to the Sponsor immediately (i.e., no more than 24 hours after learning of the event; see Section 5.4.2).

If a therapeutic or elective abortion was performed because of an underlying maternal or embryofetal toxicity, the toxicity should be classified as a serious adverse event, recorded on the Adverse Event eCRF, and reported to the Sponsor immediately (i.e., no more than 24 hours after learning of the event; see Section 5.4.2). A therapeutic or elective abortion performed for reasons other than an underlying maternal or embryofetal toxicity is not considered an adverse event.

All abortions should be reported as pregnancy outcomes on the paper Clinical Trial Pregnancy Reporting Form.

5.5 FOLLOW-UP OF PATIENTS AFTER ADVERSE EVENTS

5.5.1 Investigator Follow-Up

The investigator should follow each adverse event until the event has resolved to baseline grade or better, the event is assessed as stable by the investigator, the patient is lost to follow-up, or the patient withdraws consent. Every effort should be made to follow all serious adverse events considered to be related to study drug or [¹⁸F]GTP1 radioligand or an amyloid radioligand or trial-related procedures until a final outcome can be reported.

During the study period, resolution of adverse events (with dates) should be documented on the Adverse Event eCRF and in the patient's medical record to facilitate source data verification.

All pregnancies reported during the study should be followed until pregnancy outcome.

5.5.2 Sponsor Follow-Up

For serious adverse events, adverse events of special interest, and pregnancies, the Sponsor or a designee may follow up by telephone, fax, email, and/or a monitoring visit to obtain additional case details and outcome information (e.g., from hospital discharge summaries, consultant reports, autopsy reports) in order to perform an independent medical assessment of the reported case.

5.6 ADVERSE EVENTS THAT OCCUR AFTER THE ADVERSE EVENT REPORTING PERIOD

The Sponsor should be notified if the investigator becomes aware of any serious adverse event that occurs after the end of the adverse event reporting period (defined as 12 weeks after the final dose of study drug or 4 days after the final dose of [¹⁸F]GTP1 radioligand or an amyloid radioligand, whichever is longer), if the event is believed to be related to prior study drug or [¹⁸F]GTP1 radioligand or an amyloid radioligand treatment. If a patient discontinues the study due to an adverse event after 12 weeks after the final dose of study drug or after 4 days after the final dose of [¹⁸F]GTP1 radioligand or an amyloid radioligand, whichever is longer, the adverse event(s) leading to study discontinuation should be reported. These events should be reported through use of the Adverse Event eCRF. However, if the EDC system is not available, the investigator should report these events directly to the Sponsor or its designee, either by faxing or by scanning and emailing the paper Clinical Trial Serious Adverse Event/Adverse Event of Special Interest Reporting Form using the fax number or email address provided to investigators.

5.7 EXPEDITED REPORTING TO HEALTH AUTHORITIES, INVESTIGATORS, INSTITUTIONAL REVIEW BOARDS, AND ETHICS COMMITTEES

The Sponsor will promptly evaluate all serious adverse events and adverse events of special interest against cumulative product experience to identify and expeditiously communicate possible new safety findings to investigators, IRBs, ECs, and applicable health authorities based on applicable legislation.

To determine reporting requirements for single adverse event cases, the Sponsor will assess the expectedness of these events using the following reference document:

- MTAU9937A Investigator's Brochure
- [¹⁸F]GTP1 Investigator's Brochure
- Investigator's Brochure or prescribing information for specific amyloid radioligand used

The Sponsor will compare the severity of each event and the cumulative event frequency reported for the study with the severity and frequency reported in the applicable reference document.

Reporting requirements will also be based on the investigator's assessment of causality and seriousness, with allowance for upgrading by the Sponsor as needed.

6. STATISTICAL CONSIDERATIONS AND ANALYSIS PLAN

The efficacy analyses will be based on the modified intent-to-treat population, which is defined as all randomized patients who receive at least one dose of study drug and have at least one postbaseline ADAS-Cog11 and/or ADCS-ADL measurement. For the efficacy analysis, patients will be grouped according to the treatment assigned at randomization.

The safety analysis will be based on all randomized patients who receive at least one dose of either MTAU9937A or placebo. Patients will be grouped according to MTAU9937A treatment actually received.

- A primary analysis will occur after the last patient has completed the assessments for the last visit of the double-blind treatment period (Week 49 for Cohort 1 *or* Week 61 for Cohort 2).
- A final analysis will occur after the last patient has completed the OLE and completed the assessments for the last visit of the OLE period (Week 145 for Cohort 1 *or* Week 157 for Cohort 2).

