1.2.2 Clinical Information

The experience with MTAU9937A in humans consists of data from one completed Phase I study (GN39058), *one completed* Phase II study (GN39763), and this ongoing Phase II study (GN40040).

Study GN39058 (clinicaltrials.gov identifier NCT02820896) was a randomized, placebo-controlled, double-blind, ongoing Phase I study that assessed the safety, tolerability, and pharmacokinetics of IV and SC MTAU9937A in 65 healthy volunteers (HVs) and 10 patients with mild to moderate AD. It consisted of a single-ascending dose part (six IV cohorts, with doses from 225 mg to 16,800 mg, and one SC cohort at 1200 mg) and a multiple-dose part (two IV cohorts each receiving 8400 mg IV once a week [QW] \times 4 weeks). All single-dose cohorts consisted of only HVs; one multiple-dose cohort consisted of HVs and the other multiple-dose cohort consisted of patients with AD. The initial single-dose IV cohort consisted of 3 HVs, randomized to a 2:1 ratio (MTAU9937A:placebo). The remainder of the single-dose IV cohorts consisted of 8 HVs, randomized to a 6:2 ratio (MTAU9937A:placebo). The single-dose SC cohort consisted of 12 HVs, all treated with MTAU9937A. Each of the two multiple-dose IV cohorts consisted of 10 subjects, randomized to an 8:2 ratio (MTAU9937A:placebo). A total of 44 HVs received single doses of MTAU9937A with a range of 225–16,800 mg IV or SC (32 HVs received IV doses, 12 HVs received SC doses), and 16 participants (8 HVs and 8 patients with mild to moderate AD) each received doses of 8400 mg IV QW \times 4 (except for 1 HV, who was mistakenly administered a first dose of 4200 mg, followed by three doses of 8400 mg).

Study GN39763 was a global randomized, double-blind, placebo-controlled, parallel-group Phase II study investigating the safety and efficacy of MTAU9937A (at doses of 1500 mg, 4500 mg, or 8100 mg) in patients with prodromal to mild AD. Of the 457 patients who were randomized into treatment arms, 441 received at least one dose of MTAU9937A or placebo in the blinded portion of the study, 369 completed the blinded portion of the study, and 360 received at least one dose of MTAU9937A in the OLE portion of the study. The study was discontinued on 23 September 2020, after

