top-line analyses of data from the 73-week double-blind, placebo-controlled portion of the study indicated similar rates of progression on the primary efficacy endpoint (Clinical Dementia Rating Sum of Boxes) in the placebo arm and all three MTAU9937A arms. Similar rates of progression on the secondary efficacy cognitive endpoints (Repeatable Battery for the Assessment of Neuropsychological Status Total Index and the 13-item version of the Alzheimer's Disease Assessment Scale—Cognitive Subscale) and secondary efficacy functional endpoints (Alzheimer's Disease Cooperative Study—Activities of Daily Living and Amsterdam Instrumental Activities of Daily Living Questionnaire) were seen in the placebo arm and all three MTAU9937A arms over the 73-week treatment period. Furthermore, on the exploratory endpoint of brain tau burden as measured by fluorine-18 Genentech tau probe 1 ($[^{18}\text{F}]\text{GTP1}$) tau PET imaging, similar rates of overall cortical tau accumulation were seen in the placebo arm and all three MTAU9937A arms over the 73-week treatment period.

MTAU9937A has been generally well tolerated in HVs and patients with AD (please refer to the MTAU9937A Investigator's Brochure for further details). No adverse drug reactions have been identified with MTAU9937A. Potential risks associated with MTAU9937A are discussed in Section 5.1.1.

The pharmacokinetics of MTAU9937A were evaluated in Study GN39058 following single (225–16,800 mg), weekly (8400 mg \times 4 doses) IV, or single (1200 mg) SC administration to HVs and to patients with mild to moderate AD. Upon IV administration, MTAU9937A exhibited biphasic disposition, and the plasma half-life had a range of 22.8–45.7 days. The mean SC bioavailability estimated from the SC cohort (1200 mg) was approximately 69%. Upon weekly IV administration, the pharmacokinetics of MTAU9937A were comparable between HVs and patients with AD. Dose proportionality assessment demonstrated that serum pharmacokinetics increased proportionally with dose following single-dose IV administration. MTAU9937A was detected in the CSF, suggesting penetration into the CNS. *Pharmacokinetic results from the Phase II study (GN39763) in patients with prodromal to mild AD are consistent with PK data from HVs and patients with AD in the Phase I study (GN39058).*

Refer to the MTAU9937A Investigator's Brochure for further details on clinical studies.

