3. STUDY DESIGN

3.1 DESCRIPTION OF THE STUDY

3.1.1 Overview of Study Design and Study Treatment

This Phase II, multicenter, randomized, double-blind, placebo-controlled, parallel-group study will evaluate the clinical efficacy, safety, pharmacokinetics, and pharmacodynamics of MTAU9937A in patients with moderate AD.

The study consists of a screening period, a double-blind treatment period, an optional open-label extension (OLE) period, and a safety follow-up period (see [Figure 1](#) for the study schema and [Appendix 1–Appendix 4](#) for the schedules of activities). An extended baseline visit (up to 15 days) is included in the double-blind treatment period, following randomization and prior to the initiation of study drug. Study drug (MTAU9937A or placebo) will be administered intravenously in the double-blind treatment period, and MTAU9937A will be administered intravenously in the optional OLE period. Study drug administration will occur every 2 weeks (Q2W) for the first three doses of the double-blind treatment period and every 4 weeks (Q4W) thereafter during the double-blind treatment period. Because of anticipated disruptions in study drug administration associated with the global COVID-19 pandemic, there may be up to *two* study cohorts, as described below:

- Cohort 1: Patients who had completed or discontinued from the double-blind treatment period (i.e., completed Week 49 assessments) prior to implementation of Protocol Version 3. For Cohort 1, the Week 49 visit represents the end of the double-blind treatment period and patients will continue into the OLE or safety follow-up periods per the original schedule (see [Appendix 2](#)). In addition, patients in other cohorts who are active in the double-blind treatment period and have completed blinded study drug treatment through Week 45 without any missed doses will be eligible to revert to the Cohort 1 Schedule of Activities (see [Appendix 1](#)) at the Week 49 visit and continue to the OLE (see [Appendix 2](#)) after completing the Week 49 visit assessments.

If a Cohort 1 patient misses any blinded study drug infusion, the patient will be moved into Cohort 2.

- Cohort 2: Patients who were active in the double-blind treatment period after implementation of Protocol Version 3 were assigned to Cohort 2. In Cohort 2, the double-blind treatment period is extended to Week 61, unless the criteria above for reverting to the Cohort 1 Schedule of Activities are fulfilled.

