4.6 TREATMENT, PATIENT, STUDY, AND SITE DISCONTINUATION

4.6.1 Study Treatment Discontinuation

Patients must permanently discontinue study treatment if they experience any of the following:

- Any medical condition that the investigator or Sponsor determines may jeopardize the patient's safety if he or she continues to receive study treatment
- Investigator or Sponsor determination that treatment discontinuation is in the best interest of the patient
- Pregnancy

The primary reason for study treatment discontinuation should be documented on the appropriate eCRF. Patients who discontinue study treatment prematurely will not be replaced.

Patients will return to the clinic for a treatment discontinuation visit 12 weeks (± 7 days) after the final dose of study drug (see [Appendix 1–Appendix 4](#) for additional details).

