6.1 DETERMINATION OF SAMPLE SIZE

This study will enroll approximately 260 patients randomized to either an IV active dose arm or to an IV placebo dose arm in a 1:1 ratio. This sample size provides approximately 80% power to detect a 35% relative reduction in mean ADAS-Cog11 change from baseline when MTAU9937A is compared with placebo assuming an average decline of 6 points for placebo-treated patients, a standard deviation across patients of 7.5, a 10% dropout rate, and a two-sided $\alpha=0.2$ significance level.

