6.4 EFFICACY ANALYSES

6.4.1 Primary Efficacy Endpoints

The co-primary efficacy endpoints are change in ADAS-Cog11 and ADCS-ADL scores from baseline to the last visit of the double-blind treatment period (Week 49 for Cohort 1 *or* Week 61 for Cohort 2). The difference in mean change from baseline to the last visit of the double-blind treatment period between MTAU9937A- and placebo-treated patients will be estimated using an analysis of covariance model adjusting for *ApoE4* status (*ApoE4+* vs. *ApoE4-*), screening MMSE (16–18 vs. 19–21), baseline [¹⁸F]GTP1 PET standard uptake value ratio, age, baseline ADAS-Cog11 or ADCS-ADL scores, and if appropriate, the number of missed study drug infusions during the double-blind treatment period due to the COVID-19 pandemic. Confidence intervals, as well as least squares estimates, will be used to aid in interpretation of study results.

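### The co-primary ANCOVA uses only the last double-blind visit and, as written, has no rule for patients without a score there, so their interim scores go unused

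*Combined protocol and SAP*

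**What the plan says.** Section 6 admits to the efficacy analysis "all randomized patients who receive at least one dose of study drug and have at least one postbaseline ADAS-Cog11 and/or ADCS-ADL measurement". Nothing in that definition requires a score at the last visit.

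Section 6.4.1 names the estimate: "The difference in mean change from baseline to the last visit of the double-blind treatment period". It fixes that visit as Week 49 for Cohort 1 or Week 61 for Cohort 2 and uses an ANCOVA with baseline covariates and, if appropriate, the number of infusions missed because of the pandemic. Section 6.4.2 carries the same method to the secondary endpoints. Section 6.2 tabulates discontinuations by arm, but no efficacy analysis uses them.

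Section 6 contains no imputation rule, repeated-measures term, missing-data assumption or missing-data sensitivity analysis. A Data Analysis Plan is named once, in the safety section (6.5). The sample size in Section 6.1 treats dropout only as lost patients: "a standard deviation across patients of 7.5, a 10% dropout rate".

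On early stopping, Section 4.6.1 says: "Patients will return to the clinic for a treatment discontinuation visit 12 weeks" after the final dose. The schedule footnotes (Appendix 1, note i; Appendix 3, note j) have the scales done at that visit only if at least 16 weeks have passed since the last assessment. Section 4.5.7 allows extra remote ADCS-ADL assessments, but not ADAS-Cog11, around infusions missed because of the pandemic.

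The endpoint week can move. Section 3.1.1 says "If a Cohort 1 patient misses any blinded study drug infusion, the patient will be moved into Cohort 2", and that patients who "completed blinded study drug treatment through Week 45 without any missed doses will be eligible to revert" to the Cohort 1 schedule at Week 49.

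**The concern.** The population and the model do not match. A patient with an interim score but none at Week 49 or 61 is counted in the efficacy population and then contributes nothing to the estimate. Comparing only those who reach the last visit gives an unbiased contrast if leaving is unrelated to outcome, or related to it in the same way in both arms. If patients in one arm leave because they are declining, the remaining patients in that arm look better than the arm as a whole, and the treatment difference moves.

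The interim scores carry much of the information needed to correct this, and they are collected anyway. It is also unclear which week an early leaver is missing, because cohort membership depends on when the patient was active and on missed doses.

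**Working it through.** **Inputs.** From Section 6.1: 260 patients, 1:1; placebo decline 6 points; 35% relative reduction, so a target of 0.35 × 6 = 2.1 points; SD 7.5; 10% dropout; two-sided α = 0.2. From Section 1.2.2, for the sponsor's earlier trial: 441 dosed, of whom "369 completed the blinded portion of the study", over 73 weeks.

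**1. The plan's own figure.** Completers per arm: 130 × 0.9 = 117. Standard error: 7.5 × √(2/117) = 0.981. Power: Φ(2.1/0.981 − 1.282) = 80.5%. In reverse, 115 completers per arm are needed, or 115/0.9 = 128 randomized per arm, 256 in total. The stated power reproduces, and it is the power of a completers-only comparison.

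**2. How many patients are affected.**
- At 10%: 26 of 260. At a constant rate over 48 weeks, half leave after Week 25, so about 13 would have at least one interim score. (Week 25 as the first scheduled scale visit is read from an Appendix 1 table whose columns are broken.) Patients with no postbaseline score at all are outside the efficacy population.
- From the earlier trial: 441 − 369 = 72, and 72/441 = 16.3%. At a constant rate, 1 − (1 − 0.163)^(48/72) = 11.2% by Week 49 and 1 − (1 − 0.163)^(60/72) = 13.8% by Week 61, or 29 to 36 of 260. That trial enrolled milder patients, and completion is not reported by arm.

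**3. Bias by formula.** Let d be the dropout proportion in an arm and D the amount by which leavers' final change is worse than completers'. The completers' mean is the arm mean minus d × D. The shift in the drug-minus-placebo contrast is therefore −(d_drug × D_drug − d_placebo × D_placebo). Equal d and equal D give zero.

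**4. Simulation, ADAS-Cog11, 10% dropout.** Assumptions not in the documents: SDs of 5.5, 6.4, 7.5 and 8.7 at Weeks 25, 37, 49 and 61; linear decline; a quarter of patients finishing at Week 61; half of dropout before Week 25 and at random; the rest, in the affected arm, driven by the last observed change (logit slope 1.0 to 1.5 per SD). 1,500 replicates; Monte Carlo error of a shift about 0.01.

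| Dropout mechanism | Shift in last-visit ANCOVA |
|---|---|
| Same in both arms | 0.07 |
| Observed decline, placebo only | 0.29 to 0.38 against the drug |
| Observed decline, drug only | 0.23 to 0.28 in its favour |

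As shares of the target: 0.23/2.1 = 11% and 0.38/2.1 = 18%. A mixed model for repeated measures (MMRM) on the same data was within 0.02, as expected because the assumed mechanism suits it. At 14% dropout the one-arm shifts are 0.45 and 0.37. A simpler simulation without covariates or Week 61 gave 0.32, 0.29 and 0.07.

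**5. Error rate with no true effect.** Under one-arm dropout the ANCOVA's two-sided error is 22% to 23% against 20%, split about 17% and 6% instead of 10% and 10%.

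**6. Unequal rates.** With 15% dropout on drug and 5% on placebo, depending on the first postbaseline score (assumed correlation 0.6 with the last; slope 1 to 2 per SD), the last-visit contrast shifts by 0.37 to 0.56 points (18% to 27% of target). Using the earlier score brings this to about 0.01. Section 6.1 gives no split by arm, so this is illustration only.

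**7. Dropout driven by unobserved scores, one arm.** ANCOVA shifts 0.30 to 0.39 and MMRM still leaves 0.10 to 0.14, so about two thirds is removed. Under other assumptions the share was nearer one third.

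**8. Precision.** With equal 10% dropout and the true effect at 2.1, power was 0.81 to 0.82 for last-visit completers and 0.80 to 0.81 for a likelihood estimator using the interim score.

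**The case against.** The strongest reply is that a rule may exist. Section 6.5 refers to a Data Analysis Plan, and an efficacy population that needs only one postbaseline score suggests some handling of later gaps was intended. That stands as a limit on the claim: it concerns the protocol as written. It does not fill the gap, because the plan is named only for safety and was not available. Nor can the last visit be read as each patient's own last visit, since Section 6.4.1 names the weeks.

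A second reply is that nothing shows dropout differing by arm. Section 1.2.2 says "MTAU9937A has been generally well tolerated in HVs and patients with AD". A shared mechanism shifts the contrast by only 0.07 points, and a two-point rise in a 20% error rate is tolerable in a study that calls itself hypothesis-generating. This is fair, and it limits the size of the point. It does not justify leaving the handling unstated, since the remedy uses scores already collected.

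A reader might also infer, from the 12-week discontinuation visit and the 16-week condition, that no Cohort 1 early discontinuer can have a Week 49 score. The documents do not support that. The schedule table is broken in the available text, Section 4.6.1 does not say scheduled visits stop after discontinuation, and Section 3.1.1 describes the Cohort 1 patients who completed or discontinued as having completed Week 49 assessments.

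Finally, the amendment rationale reports no double-blind effect on tau PET, and Section 5.1.1.2 cites unblinded safety data from this study. Changing the primary model now may be post hoc. That stands and shapes the fix.

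**Conclusion.** The point holds for the protocol as written. The co-primary analysis is observed-case by default, leaves interim scores unused, and is undefined for up to about one patient in ten. The shift of 0.23 to 0.38 points depends on assumed visit SDs, linear decline and observed-decline dropout confined to one arm. It covers ADAS-Cog11 only, because the documents give no planning figures for ADCS-ADL.

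A reader might infer that the treatment effect is biased. The documents do not show that: they give no dropout by arm, and the expected bias is near zero if the arms behave alike. A reader might also infer that the contrast should move to Week 49 for everyone. Missing-data handling does not require it, and it would replace the protocol's stated Week 61 endpoint for Cohort 2. The power calculation in Section 6.1 is not in error.

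**What to change.** If double-blind results are still blinded, amend Section 6.4.1 as follows, or cite the Data Analysis Plan if it already does this:

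- Keep the endpoint (last double-blind visit, Week 49 or 61 by cohort) and the stated covariates.
- Estimate the difference with a method that uses all scheduled double-blind scores: either an MMRM, or multiple imputation of the missing last-visit score from the interim scores followed by the stated ANCOVA. Imputation leaves the final model unchanged. With an MMRM, also state how the two endpoint weeks are combined.
- Set an early leaver's endpoint week by the cohort schedule in force when the patient discontinued.
- State how discontinuation-visit scores, taken 12 weeks after the last dose, and remote ADCS-ADL scores are used.
- Add one missing-not-at-random sensitivity analysis, delta-adjusted or reference-based, because the main method removes only part of the bias when dropout depends on unseen scores.

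If results are already unblinded, keep the ANCOVA as primary, label it observed-case, and report the MMRM or imputation analysis and the missing-not-at-random analysis as labelled sensitivity analyses.

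The cost is extra programming and text, and a main estimate that rests on a missing-at-random assumption. Precision is about the same, and no new visits or data are needed.
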